3. STUDY RATIONALE

3.1. Study Rationale

Preclinical and preliminary clinical information, as discussed above, strongly suggests that the primary pathophysiologic mechanism in AA (including AT and AU) is a cytokine-mediated (primarily through T-lymphocyte induced upregulation of IL-15 and IFN gamma) induction of and prolonged maintenance of the telogen stage of the hair cycle. Inhibitors of the JAK/STAT pathway, particularly JAK1 and JAK3, are known to downregulate the effects of both IFN-gamma (through the inhibition at JAK1), and IL-15 (through inhibition at both JAK1 and JAK 3), and several published case reports have demonstrated the potential for compounds that are JAK1/3 inhibitors to induce hair growth in patients with AA. As ATI-50002 is a potent inhibitor at JAK 1 and JAK 3, it is strongly suggested that ATI-50002 may be effective in the treatment of AA.

Topical treatment with ATI-50002 Topical Solution on the areas of a patient's scalp with alopecic patches only may result in undertreatment of disease and potentially lead to sub-optimal efficacy. Discussion with experts in the treatment of alopecia has led Aclaris to the conclusion that by only treating sites of visible disease, areas of sub-clinical, but active disease may be untreated. These sub-clinical patches may either (a) develop into new patches of disease, or (b) harbor a focus of inflammation that impacts other sites on the scalp.

Patchy Alopecia Areata can be a frustrating disease, both to the patient and prescriber. Physicians tell of disease that they describe as "whack a mole", meaning that treatment can be successful in one patch, only for new patches to emerge elsewhere. Reviews describe how regrowth in one region of the scalp may be associated with expanding areas of alopecia elsewhere (Pratt, 2017). This dynamic picture of disease suggests that areas of seemingly non-active disease likely have sub-clinical ongoing auto-immune inflammation.

If areas of untreated inflammation are present, the question is whether they can impact the health of other areas of scalp. The C3H/HeJ mouse model of alopecia provides strong evidence that disease in one area of skin can indeed impact another (McElwee, 1998). In this model, an alopecia phenotype is transmitted when skin from alopecia affected mice is grafted onto normal C3H/HeJ mice. This implies that the inflammatory process at one site can spread and lead to disease at another. Consequently, subjects in this study will be instructed to apply study medication to the entire scalp twice-daily to increase the probability that patients with patchy alopecia in ATI-50002-AA-201 will achieve good efficacy.

This study will evaluate the safety, tolerability and efficacy of ATI-50002 Topical Solution, 0.12% and 0.46% compared to vehicle solution applied twice-daily to the entire scalp for 6 months. In addition, at select clinical sites, the study will explore the effects of ATI-50002 induced Janus kinase (JAK)1/3 inhibition on the ALADIN scores, peribulbar infiltrate and other inflammatory biomarkers from scalp biopsies and blood samples. The Alopecia Areata Disease Activity Index (ALADIN) is a three-dimensional quantitative composite gene expression score that will be used in this study to track disease severity and explore signs of response to treatment (Xing et al 2014).

Subjects with patchy scalp hair loss due to AA ranging from 15% to 95% based on the SALT score will be included in this study. In prior published studies, assessment of efficacy of treatment of AA was based on hair regrowth as determined by changes in the SALT score (Olsen 2016). Both the SALT and ALODEX scores will be measured electronically using an iPad. The SALT score is a measurement based on the SALT I diagram, that quantifies the amount of scalp without any hair. The ALODEX score is a measurement of the amount of scalp with hair loss and is based on the SALT II diagram (Olsen, submitted). The SALT II diagram breaks the scalp surface area from the SALT I diagram into 1% scalp surface areas and allows the investigator to assign a density rating to each area from 0 = no hair loss to 100 = complete baldness. The ALODEX score is a summation of all density ratings in each 1% scalp area. By assessing hair density in each of the 1% scalp areas, the use of the SALT II visual aid allows the following to be tracked: amount of absolute hair loss (ALODEX score), specific areas of baldness (all 1% areas are numbered), small changes in density that may otherwise go undetected with original SALT I score, percentage of scalp surface involved with any hair loss and thus needing to be treated topically, new areas of hair loss present since baseline of any given treatment, and lesional scoring by identifying target areas.

Hair loss will be quantified using both the SALT and ALODEX assessments at baseline and monthly during treatment. The change from baseline in the SALT and ALODEX scores will be used to determine hair regrowth. In addition to the SALT and ALODEX assessment tools, Aclaris is developing Clinician and Patient Reported outcome tools (ClinRO and PRO) to assess hair regrowth that is clinically meaningful to subjects.

These ClinRO and PRO tools will measure the signs, symptoms, and impacts of AA for use as secondary efficacy endpoints. The following PRO and ClinRO questionnaires designed to measure the scalp appearance, the impact and the global satisfaction with treatment from the perspective of the patient and the clinician, where appropriate, are included in the protocol:

- Scalp based appearance PRO and ClinRO
 - Alopecia Scalp Appearance Assessment (AAA) for Patchy AA: Subject Rating [SR]

- Alopecia Scalp Appearance Assessment (AAA) for Patchy AA: Clinician Rating [CR]
- Impact of alopecia PRO
 - Alopecia Impact Assessment (AIA)
- Satisfaction with treatment PRO
 - Subject Global Impression of Treatment Satisfaction (SGITS)

Subjects will be enrolled with a range of 15% to 95% hair loss over the entire scalp surface area based on the SALT score at baseline. A baseline ALODEX score will also be obtained but will not be used as an inclusion criterion. The scalp appearance assessments in development (ClinRO and PRO) will assess hair loss on a scale from “no hair” to a “full head of hair”. A target patch (identified by the subject as their most bothersome area of hair loss) will be identified at baseline. By identifying a target patch, subjects with less extensive hair loss overall can be enrolled using the same rating on the Alopecia Scalp Appearance Assessment of “no hair” or “a little hair” at baseline. In addition to the ClinRO and PRO assessments being completed for a target patch, the same scalp appearance assessments will be completed for hair loss over a subject’s entire scalp surface area.

Because this trial will not be stratified in terms of ethnic background or gender of subjects, there is no consistent measure of hair color, caliber, growth rate or hair density that can be used across such a diverse population of subjects. Each of these parameters is intrinsically determined within a given subject, and in subjects with more severe hair loss, there will be little to no normal hair at the start of the study. Therefore, it will be impossible to establish each subject’s individual baseline measure of healthy hair in order to monitor restoration of these parameters over the study. Further, it is not possible to compare these parameters across individuals in the study.

The ALODEX and SALT assessments are based on terminal hair growth. Another parameter that will be considered will be the normalization of exclamation point hairs. These two features should be trackable irrespective of the subjects’ intrinsic hair color, caliber or density, and should give a meaningful indicator of response to treatment.

The 6-month topical treatment period is supported by the results of 26-week mouse and 39-week dog oral toxicity studies with systemic administration and a 6-month update from the 9-month minipig study with dermal administration.

4. STUDY OBJECTIVES

4.1. Primary Objective

The primary objective is to assess the safety, tolerability and efficacy of ATI-50002 Topical Solution, 0.46% and 0.12% compared to vehicle in subjects with stable patchy alopecia areata (AA).

4.2. Secondary Objectives

Secondary objectives are:

- To evaluate the psychometric performance of the key clinical outcome assessments questionnaires with respect to reliability, construct-related validity, and sensitivity to change
- To generate score interpretation estimates for the clinical outcome assessments to guide the definition of responders in pivotal trials

4.3. Exploratory (Select Sites Only):

At select clinical sites, to explore the effects of ATI-50002 induced Janus kinase (JAK) 1/3 inhibition on the ALADIN scores, peribulbar infiltrate and other inflammatory biomarkers.

4.4. Long-term Objective

To assess the safety, tolerability and efficacy of ATI-50002 Topical Solution, 0.46% in subjects with stable patchy alopecia areata.

5. SELECTION AND DISPOSITION OF STUDY POPULATION

5.1. Number of Subjects and Study Sites

A total of 120 subjects will be enrolled at approximately 27 US sites.

5.2. Study Population Characteristics

Male and female subjects, 12 years of age or older, with a clinical diagnosis of stable patchy alopecia areata of the scalp, who meet all the inclusion criteria and none of the exclusion criteria, will be eligible to enroll in this study.

5.3. Double-Blind Inclusion Criteria

Subjects must meet the following criteria to be eligible for participation in the study:

1. Able to comprehend and willing to sign an Informed Consent/Accent Form (ICF).
2. Male or non-pregnant, non-nursing female ≥ 12 years old at the time of informed consent/assent.
3. Have a clinical diagnosis of stable patchy alopecia areata (AA) defined as no current areas of spontaneous regrowth.
4. Have a Severity of Alopecia Tool (SALT) score of at least 15% up to 95% total scalp hair loss determined by the study investigator at baseline.
5. Have an assessment of “no hair” or “a little hair” in the target scalp patch based on both the Clinician and Subject Alopecia Scalp Appearance Assessment (AAA).
6. Have a duration of the current episode of scalp hair loss of a minimum of 6 months and a maximum of 12 years.
7. If a woman of childbearing potential (WOCBP), must have a negative serum pregnancy test at Screening (Visit 1) and a negative urine pregnancy test at Baseline (Visit 2) and agree to: use a highly effective method of birth control for the duration of the study; not be planning a pregnancy during the study duration and use contraception for 30 days after last application of study medication. (Refer to Section 10).

8. Be in good general health and free of any known disease state or physical condition which, in the investigator's opinion, might impair evaluation of the subject or which might expose the subject to an unacceptable risk by study participation.
9. Be willing to maintain the same hair style throughout the study period. Subjects who shave their scalp must be willing to refrain from shaving their scalp for at least one week or longer prior to each study visit, as determined by the investigator based on visible scalp hair growth. Hair trimming outside the treatment areas to maintain the current hair style is permitted.
10. Be willing and able to follow all study instructions and to attend all study visits.
11. Subjects taking hormonal replacement therapies must be on stable doses for 6 months prior to enrollment and remain on the same maintenance dose throughout the study.
12. Subjects taking thyroid replacement medication must be on stable doses for 6 months prior to enrollment and remain on the same maintenance dose throughout the study.
13. Sexually active male subjects must agree to use a barrier method of contraception from the first application of study medication to at least 30 days after the last application of study medication.

5.4. Double-Blind Exclusion Criteria

Subjects are excluded from this study if any 1 or more of the following criteria is met:

1. Females who are nursing, pregnant, or planning to become pregnant for the duration of the study and up to 30 days after the last application of study medication.
2. Diffuse alopecia areata.
3. Concomitant hair loss disorder (by history or physical exam) such as androgenetic alopecia, or scarring alopecia (*e.g.*, cicatricial alopecia, frontal fibrosing alopecia, etc.). Subjects without prior known history of androgenic alopecia (AGA) or other patterned hair loss disorder, who exhibit AGA or other patterned hair loss with regrowth during the study, will be allowed to continue in the study.
4. Active skin disease on the scalp (such as psoriasis or seborrheic dermatitis) or a history of skin disease on the scalp that in the opinion of the investigator would interfere with the study assessments of efficacy or safety.
5. Active scalp trauma or other condition affecting the scalp that, in the investigator's opinion, may affect the course of AA or interfere with the study conduct or evaluations.
6. The presence of a permanent or difficult to remove hairpiece or wig that will, in the opinion of the investigator, interfere with study assessments if not removed at each visit.
7. History of, or current, severe, progressive or uncontrolled renal, hepatic, gastrointestinal, pulmonary, cardiovascular, genitourinary (renal disease) or hematological disease, neurologic or cerebral disorders, infectious disease or coagulation disorders that, as determined by the Investigator, would preclude participation in and completion of study assessments.
8. History of, current or suspected systemic or cutaneous malignancy and /or lymphoproliferative disease, other than subjects with: a history of adequately treated and well healed and completely cleared non-melanoma skin cancers (basal or squamous cell carcinoma) treated successfully at least 1 year prior to study entry with no evidence of disease.
9. Evidence of active or latent bacterial (including tuberculosis) or viral infections at the time of enrollment or history of incompletely treated or untreated tuberculosis. Subjects who have completed therapy for latent tuberculosis may participate.

10. History of a serious local infection (e.g., cellulitis, abscess) or systemic infection including but not limited to a history of treated infection (e.g., pneumonia, septicemia) within 3 months prior to Baseline (Visit 2). Subjects on an antibiotic for a nonserious, acute local infection must complete the course prior to enrollment into the study.
11. Positive for HIV, Hepatitis B or C. Subjects with serologic evidence of Hepatitis B vaccination (Hep B surface Ab without the presence of Hep B sAg) will be allowed to participate.
12. Herpes zoster or cytomegalovirus (CMV) that resolved less than 2 months before study enrollment. Subjects with a history of frequent outbreaks of Herpes Simplex Virus (defined as 4 or more outbreaks a year).
13. Clinically significant laboratory abnormalities at screening that, in the opinion of the Investigator, would make the subject a poor candidate for the study.
14. Subjects with absolute neutrophil count <1,800/mL or platelet count <130,000/mL.
15. Subject unable to comply with the following required washout periods:

Therapy/Medication	Washout Period
Systemic Therapies	
Disease Modifying Anti-Rheumatic Drugs (DMARDs), Biologics or immunosuppressants, such as: anakinra, adalimumab, azathioprine, corticosteroids, cyclosporine, etanercept, infliximab, methotrexate, TNF inhibitors, ustekinumab	1 month or 5 half-lives whichever is greater
Plaquenil	2 months
JAK inhibitors (oral or topical)	6 months
Intralesional Steroids (Scalp)	
Topical Treatments on the Scalp	
Anthralin, bimatoprost, corticosteroids, diphencyprone, diphenylcycloprophenone (DPCP), Squaric acid dibutylester (SADBE), minoxidil, pimecrolimus, tacrolimus	1 month
Phototherapy, Laser Therapy, Excimer Laser	3 months

16. Participation in an investigational drug or device trial in which administration of an investigational study drug or device occurred within 30 days or 5 half-lives (whichever is longer) of Screening (Visit 1). Subjects who have participated in a study of an investigational drug, device or biologic agent for alopecia areata within 1 year of screening will be eligible to participate only with individual permission from the Medical Monitor.
17. Sensitivity to any of the ingredients in the study medications.
18. History of or current alcohol or drug abuse within 2 years of assessment for study enrollment.

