12. Herpes zoster or cytomegalovirus (CMV) that resolved less than 2 months before study enrollment. Subjects with a history of frequent outbreaks of Herpes Simplex Virus (defined as 4 or more outbreaks a year).
13. Clinically significant laboratory abnormalities at screening that, in the opinion of the Investigator, would make the subject a poor candidate for the study.
14. Subjects with absolute neutrophil count <1,800/mL, or platelet count <130,000/mL.
15. Subject unable to comply with the following required washout periods:

Therapy/Medication	Washout Period
Systemic Therapies	
Disease Modifying Anti-Rheumatic Drugs (DMARDs), Biologics or immunosuppressants, such as: anakinra, adalimumab, azathioprine, corticosteroids, cyclosporine, etanercept, infliximab, methotrexate, TNF inhibitors, ustekinumab	1 month or 5 half-lives whichever is greater
Plaquenil	2 months

JAK inhibitors (oral or topical)	6 months
Intralesional Steroids (Scalp)	1 month
Anthralin, bimatoprost, corticosteroids, diphenycprone, diphenylcycloprophenone (DPCP), Squaric acid dibutylester (SADBE), minoxidil, pimecrolimus, tacrolimus	1 month
Phototherapy, Laser Therapy, Excimer Laser	3 months

16. Participation in an investigational drug or device trial in which administration of an investigational drug or device occurred within 30 days or 5 half-lives (whichever is longer) of Screening (Visit 1). Subjects who have participated in a study of an investigational drug, device or biologic agent for alopecia areata within 1 year of screening will be eligible to participate only with individual permission from the Medical Monitor.

17. Sensitivity to any of the ingredients in the study medications.

18. History of or current alcohol or drug abuse within 2 years of assessment for study enrollment.

19. Unwillingness to refrain from weaves, hair extensions, or shaving of the scalp for at least one week or longer prior to each study visit, as determined by the investigator based on visible scalp hair growth for the duration of the study.

20. Screening ECG findings of:

- QTcF >450msec for males or >470msec for females (use of the ECG algorithm is acceptable for this purpose)
- Clinically Significant Heart rate < 45 or Heart Rate > 100 beats/minute
- Rhythm disturbance other than sinus arrhythmia or ectopic supraventricular rhythm (ectopic atrial rhythm)
- Conduction disturbance including PR >240msec, pre-excitation (delta wave and PR <120msec), second degree or higher AV block

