5.5.1. OLE Entry Criteria

1. Subject must be able to comprehend and willing to sign the OLE Informed Consent/Accent Form (ICF).
2. Subject must continue to meet the entry criteria from the double-blind period. The SALT score and duration of disease are based on the double-blind period baseline visit.
3. Subject has not experienced any clinically significant AEs, SAEs or tolerability issues that met the study discontinuation criteria in the double-blind period.
4. Subject is capable of regrowing scalp hair in the opinion of the investigator.
5. WOCBP must have a negative UPT at entry into OLE.

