8.4.3. Clinical Laboratory Assessments

A qualified staff member will collect non-fasting samples for clinical laboratory analysis at screening and baseline and then monthly throughout the study. Samples will be sent to ACM Global Laboratories for analysis. Refer to the study specific laboratory manual for handling and shipping instructions. The following tests will be conducted:

Chemistry Panel	Complete Blood Count
Albumin	Hematocrit
Alkaline phosphatase	Hemoglobin
Alanine aminotransferase (ALT)	Platelet count
Aspartate aminotransferase (AST)	Red blood cell morphology
Blood urea nitrogen (BUN)	Red blood cell count
Bicarbonate	White blood cell count
Calcium	White blood cell differential
Chloride	% & absolute
Creatinine	Basophils
Glucose	Eosinophils
Lactate dehydrogenase (LDH)	Lymphocytes
Phosphorus	Monocytes
Potassium	Neutrophils
Sodium	

Total bilirubin	Urinalysis
Total protein	
Uric acid	
Total cholesterol, LDL, HDL,	
Triglycerides	
Creatine Phosphokinase (CPK)	
Screening Only	
Virology (HepB, HCV, HIV)	
Quantiferon Gold	
Total Iron Binding Capacity (TIBC)	
Serum iron	
Serum Ferritin	
T3/T4, TSH	
Serum pregnancy	

The following clinical laboratory tests: TIBC, serum iron, serum ferritin, T3/T4, TSH are drawn at screening to rule out any underlying conditions that could be causing alopecia. The results of the clinical laboratory tests will be reported on ACM Global Laboratory's standard reports. The investigator must note NCS or CS to define the clinical relevance of any result that is outside the normal range for the laboratory. The investigator must date and initial every laboratory report. The investigator or subinvestigator must review all the Screening (Visit 1) laboratory test results against the study entry criteria for each subject prior to Baseline (Visit 2). The investigator must report all laboratory results that are BOTH outside the normal range for the laboratory AND, in the opinion of the investigator, CS as medical history if found prior to the first study medication treatment or as an AE if found after the first study medication treatment begins. Throughout the study, the investigator must review all laboratory reports in a timely manner.

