9.2.4.2 Study Medication Discontinuation

Study medication should be permanently discontinued in the event of any of the following:

- Severe infection requiring parenteral antimicrobial therapy or hospitalization
- Symptomatic herpes zoster
- Malignancy – except for non-melanoma skin cancer (SCC or BCC) not in or near the treatment area
- Anaphylactic or severe allergic reaction
- WBC Count: $< 1 \times 10^9/L$ or second occurrence of $< 2 \times 10^9/L$
- ANC: $< 0.5 \times 10^9/L$ or second occurrence of $< 1 \times 10^9/L$
- Lymphocyte count: $< 0.3 \times 10^9/L$ or second occurrence of $< 0.5 \times 10^9/L$
- Platelet count: $< 50 \times 10^9/L$ or second event of $< 75 \times 10^9/L$ - in each case, value should be confirmed by retesting before treatment discontinuation

- Hemoglobin: < 6.5 g/dL or second occurrence of < 8 g/dL - in each case, value should be confirmed by retesting before treatment discontinuation
- AST or ALT:
 - > 5 x ULN persisting for 2-weeks of study medication interruption or second event of > 5 x ULN
 - > 3 x ULN with total bilirubin > 2 x ULN or symptoms of hepatocellular injury (fatigue, nausea, vomiting, right upper quadrant pain or tenderness, fever, rash and/ or eosinophilia (>5%).
- Serum creatinine: > 2 x ULN persisting for > 2 weeks of treatment discontinuation or second occurrence of > 2 x ULN

The continued treatment of subjects who experience other serious or severe adverse events considered related to study treatment should be discussed with the Sponsor's medical monitor.

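### Exclusion 14 gives its neutrophil and platelet limits per mL, a thousand-fold unit error that puts the entry limits below the protocol's own stopping limits

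*Protocol*

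**What the plan says.** Item 14 of the double-blind exclusion criteria (Protocol Section 5.4) rules out "Subjects with absolute neutrophil count <1,800/mL or platelet count <130,000/mL". The Synopsis repeats it with one added comma: "Subjects with absolute neutrophil count <1,800/mL, or platelet count <130,000/mL". No current text corrects the unit, and the SAP does not restate the limits.

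The on-study haematology rules use a different unit, x10^9/L. Table 2 in Section 9.2.4.1 holds treatment at ANC below 1 or platelets below 75, and allows it to resume at 1.5 and 100 or above. Section 9.2.4.2 stops treatment permanently at ANC below 0.5 or platelets below 50, or on a second fall below the hold limit.

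Item 14 is used in three further places:

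- Section 8.4.3 has the investigator or subinvestigator compare screening laboratory results with the entry criteria before Baseline.
- Section 5.5.1 carries the criteria into the open-label extension: "Subject must continue to meet the entry criteria from the double-blind period".
- Protocol Section 11.2 and SAP Section 4.3 both treat an unmet eligibility criterion as a major violation that removes a subject from the per-protocol population.

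**The concern.** An entry limit for a blood count should be at least as strict as the limit at which treatment is withheld. Otherwise a subject can be randomised while already meeting a hold or stopping rule. As printed, item 14 is far looser than either.

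It is also the only numeric haematology limit at entry. Applied literally, it leaves low counts to clinical judgement. If some sites apply it literally and others silently read it per microlitre, the same subject could be eligible at one site and ineligible at another, both at screening and at entry to the extension. The same subject could also be classed differently for the per-protocol population.

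**Working it through.** The entry limits are stated in the protocol, not derived, so there is no planned figure to reproduce. The check is a unit conversion followed by a comparison with Section 9.2.4.

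**Inputs.** Entry limits of 1,800 and 130,000 per mL (Section 5.4 and Synopsis, item 14). Hold limits of 1 and 75, and resume limits of 1.5 and 100 (Table 2). Permanent stopping limits of 0.5 and 50 (Section 9.2.4.2). All on-study limits are in x10^9/L.

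**As printed.** Value per mL x 1,000 mL/L, divided by 10^9:

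- ANC: 1,800 x 1,000 = 1.8 x10^6/L = 0.0018 x10^9/L
- Platelets: 130,000 x 1,000 = 1.3 x10^8/L = 0.13 x10^9/L

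**Per microlitre.** Value x 10^6 microlitres/L, divided by 10^9:

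- ANC: 1,800 x 10^6 = 1.8 x10^9/L
- Platelets: 130,000 x 10^6 = 130 x10^9/L

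**Comparison (all x10^9/L).**

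| | Entry, as printed | Entry, per microlitre | Resume | Hold | Stop permanently |
|---|---|---|---|---|---|
| ANC | 0.0018 | 1.8 | 1.5 | 1 | 0.5 |
| Platelets | 0.13 | 130 | 100 | 75 | 50 |

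As printed, the entry limits are below the hold limits by factors of 1/0.0018 = 556 (ANC) and 75/0.13 = 577 (platelets). They are below the permanent stopping limits by 0.5/0.0018 = 278 and 50/0.13 = 385. Per microlitre, each row falls in the expected order: entry, resume, hold, stop. The entry limits are then 1.8/1.5 = 1.2 and 130/100 = 1.3 times the resume limits.

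**Subjects for whom the reading matters.**

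- ANC 1.2 x10^9/L is 1,200,000 per mL, or 1,200 per microlitre. It passes item 14 as printed (1,200,000 > 1,800) and fails it per microlitre (1,200 < 1,800). It triggers no hold (1.2 is not below 1).
- Platelets 100 x10^9/L is 100,000,000 per mL, or 100,000 per microlitre. It passes as printed (100,000,000 > 130,000) and fails per microlitre (100,000 < 130,000). It triggers no hold (100 is not below 75).
- ANC 0.4 x10^9/L is 400,000 per mL. It passes as printed although it is already below the permanent stopping limit of 0.5.

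In the first two cases the on-study rules would not bring a literal site and an inferring site back into agreement.

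**The case against.** The strongest objection is that the error may not be in the protocol at all. The text available was read from a PDF, and a micro sign is easily read as the letter m. Other Greek letters survive in the Protocol (gamma in Section 2.1, beta in Section 8.4.4), but no micro sign appears anywhere in either document, so nothing shows that one would have survived. The two exclusion lists are near-duplicates, so the second occurrence is not independent confirmation. This objection stands. It is why the source should be checked first and why confidence is only medium.

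A second objection concerns intent. The Amendment History for Version 4.0 says the ANC and platelet criteria were moved to below the lower limit of normal, which suits 1.8 and 130 x10^9/L. The documents give no laboratory reference ranges, however, so the match cannot be verified. This is fair, and the conclusion does not need it: the ordering against Section 9.2.4 is enough.

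Third, the consequence is slight. The printed limits are so low that a reader would suspect a slip. Item 13 still excludes "Clinically significant laboratory abnormalities at screening that, in the opinion of the Investigator, would make the subject a poor candidate for the study". Exclusion 7 and inclusion 8 also rest on judgement, and Section 8.4.3 adds that "The investigator must note NCS or CS to define the clinical relevance of any result that is outside the normal range for the laboratory". Table 2 itself tolerates dosing at ANC 1.0 to 1.8 and platelets 75 to 130 x10^9/L. Subjects reaching the extension have had monthly blood counts under the hold and stopping rules. All this is correct and sets the severity. But these safeguards at entry are discretionary and do not replace the objective limit the sponsor chose to write.

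**Conclusion.** The concern holds. If the source document prints mL, item 14 is wrong by a factor of 1,000 in both places: 0.0018 and 0.13 x10^9/L as written, against 1.8 and 130 x10^9/L as evidently intended. Taken literally, it does not do its job.

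Severity is minor. Where subjects with counts between the hold limits and the intended entry limits are admitted, their exposure is within what the protocol already tolerates on study. The primary intent-to-treat analysis is unaffected, and any effect on the per-protocol population is small.

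The conclusion rests on two assumptions: that the extracted unit is what the protocol prints, and that the sponsor meant the entry limits to sit above the on-study limits.

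**What to change.** Check the source PDF first. If it shows a micro sign, nothing needs to change. If it shows mL, rewrite item 14 in the Synopsis and in Section 5.4 to exclude subjects with ANC <1.8 x10^9/L or platelet count <130 x10^9/L, so that the entry and on-study limits share one unit.

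The cost is a unit correction in two places, by administrative letter or with the next amendment. Data collection and analysis do not change.
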